5.1 Study Visits

Perform study procedures as referenced in the Schedule of Study Assessments and Procedures (see protocol synopsis) in the order specified below.

5.1.1 Screening

- Informed consent
- Medical/ocular and concomitant medication history, with review of inclusion/exclusion criteria
 - Any unfavorable medical occurrence should be reported as medical or ocular history
- BCVA
- Biomicroscopy
- Goldmann tonometry
- Gonioscopy
- Pachymetry
- Dilated ophthalmoscopy
- At any time during the visit after informed consent:
 - Urine pregnancy test (if applicable); result must be negative
 - Visual field testing

5.1.2 Day 0

- Medical/ocular and concomitant medication history, with review of inclusion/exclusion criteria
- Urine pregnancy test (if applicable, at any time during the visit); result must be negative
- Any unfavorable medical occurrence should be reported as medical or ocular history
- Heart rate/blood pressure at all required timepoints
- BCVA (may be performed prior to heart rate/blood pressure)
- Biomicroscopy
- Conjunctival hyperemia grading at all required timepoints
- Goldmann tonometry at all required timepoints

5.1.3 Day 1

- Medical/ocular and concomitant medication history, with review of inclusion/exclusion criteria (and again after Pre-T₀ Goldmann tonometry)
- Any pre-dose unfavorable medical occurrence should be reported as medical or ocular history
- Heart rate/blood pressure at all required timepoints
- BCVA(may be performed prior to heart rate/blood pressure)
- Biomicroscopy at all required timepoints
- Conjunctival hyperemia grading at all required timepoints
- Goldmann tonometry at all required timepoints
- Randomization and IP administration immediately after 8 AM T₀ IOP timepoint
- Any post-dose unfavorable medical occurrence should be reported as an Adverse Event

5.1.4 Days 7 and 14

Concomitant medications

- Adverse events
- IP compliance
- BCVA(may be performed prior to heart rate/blood pressure)
- Biomicroscopy at all required timepoints (i.e., Pre-T₀)
- Conjunctival hyperemia grading at all required timepoints (i.e., Pre-T₀)
- Goldmann tonometry (Pre-T₀)
- IP administration (8 AM only)

5.1.5 Day 28

- Concomitant medications
- Adverse events
- IP compliance
- Heart rate/blood pressure at all required timepoints
- BCVA(may be performed prior to heart rate/blood pressure)
- Biomicroscopy at all required timepoints
- Conjunctival hyperemia grading at all required timepoints
- Goldmann tonometry at all required timepoints
- IP administration (8 AM only)
- Urine pregnancy test (if applicable) at any time during the visit
- Dilated ophthalmoscopy after final Goldmann tonometry may be performed on following day for scheduling convenience.

6. ASSESSMENT OF EFFICACY

6.1 Efficacy Parameters

Primary Efficacy Endpoints:

The primary efficacy measure will be the mean change in IOP from Baseline (Day 1) IOP (mmHg) for each group on Day 28 at each matched time point as compared to timolol. IOP will be measured according to the Schedule of Assessments and Procedures Table.

Secondary efficacy endpoints:

- 1. The observed IOP, mean change from Baseline, and % change from Baseline IOP at each matched time point at each visit, and
- 2. The mean observed, mean change from Baseline and mean % change from Baseline for the mean diurnal IOP at each visit, and
- 3. The proportion of subjects with IOP \leq 18 mmHg at each time point at each visit, and with the mean diurnal IOP \leq 18 mmHg for each visit.

6.2 Method and Timing

The efficacy parameter for this study is IOP as measured by Goldman applanation tonometry. The timing of the IOP measurements is based on standard diurnal measurements, and data from the previous clinical study of H1337.

7. ASSESSMENT OF SAFETY

7.1 Adverse Event Reporting

The investigator is responsible for monitoring the safety of subjects who have entered the study. Subjects should be asked at each visit about any changes in their health status. Any changes in health status after informed consent has been obtained, but prior to the first dose of IP, will be reported as medical history. Changes will be reported as AEs after the subject receives the first dose of IP (Day 1). Ongoing AEs at study completion (Day 28) or the final study visit will be followed until the event resolves, stabilizes, or for 30 days, whichever comes first.

All adverse events (serious and non-serious) must be documented regardless of the causal relationship to the study medication. The severity, frequency, seriousness, duration, relationship to IP(s), treatment of event, action taken with IP, and outcome for every adverse event should be documented.

Non-clinically significant incremental < 2 unit grade changes in conjunctival hyperemia (according to the photographic reference scale provided for the trial) are not required to be reported as adverse events; changes ≥2 unit grade changes must be reported as an Adverse Event and tracked until returning to baseline.

To capture the most potentially relevant safety information during a clinical study, it is important that investigators record accurate AE terms. Wherever possible, a specific disease or syndrome rather than individual associated signs and symptoms should be identified by the investigator and recorded. However, if an observed or reported sign or symptom is not considered a component of a specific disease or syndrome by the investigator, it should be recorded as a separate AE.

Investigators are required to report to D. Western Therapeutics, Inc. or its representative all observed and/or volunteered AEs occurring during the clinical trial (21 CFR §312.64[b]) regardless of treatment group or suspected causality to the investigational drug.

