- 30. Women of childbearing potential who are pregnant, nursing, planning a pregnancy, or not using a medically acceptable form of birth control. An adult woman is considered to be of childbearing potential unless she is one year post-menopausal or three months post-surgical sterilization. All females of childbearing potential must have a negative urine pregnancy test result at the Screening Visit and at Baseline (Day 1) prior to randomization in the study and must not intend to become pregnant during the study.
- 31. History of drug or alcohol abuse within the last 5 years.
- 32. Unwillingness to refrain from consumption of alcohol or cannabinoids, including tetrahydrocannabinol (THC) and cannabidiol (CBD), in any form by any delivery route, on

the day prior to each study visit after Visit 1 Screening. 33. Related to site study staff and/or site employees.	1 1 1 1 1 1 0 771 1 2 7
33. Related to site study staff and/or site employees.	the day prior to each study visit after Visit 1 Screening.
	33. Related to site study staff and/or site employees.
	a is a second of the second of

Table 1. Time and Events Schedule

Assessments/Procedures ¹	Screening (-49 to 1 days)	Day 0 (-4 to -1)	Day 1 Baseline/Randomization	Day 7 (± 1 day)	Day 14 (± 1 day)	Day 28 (± 2 days) Last Dosing Day
	Visit 1	Visit 2	Visit 3	Visit 4	Visit 5	Visit 6
Informed Consent	X					
Medical and Ocular History	X	X	X			
Concomitant Medications/Procedures	X	X	X	X	X	X
Adverse Event Assessments	X	X	X	X	X	X
Randomization			X			
IP Administration in Office (AM dose) ²			X (T ₀)	X (T ₀)	X (T ₀)	$X \ (T_0)$
Assess IP Compliance				X	X	X
Heart Rate/Blood Pressure (± 30 min)		$X \\ Pre-T_0 \\ T_0+1 \ hr \\ T_0+2 \ hrs \\ T_0+4 \ hrs \\ T_0+8 \ hrs \\ T_0+12 \ hrs^3$	X Pre-T ₀ $T_0 + 1 \text{ hr}$ $T_0 + 2 \text{ hrs}$ $T_0 + 4 \text{ hrs}$ $T_0 + 8 \text{ hrs}$ $T_0 + 12 \text{ hrs}^3$		X Pre-T ₀	$X \\ Pre-T_0 \\ T_0 + 1 hr \\ T_0 + 2 hrs \\ T_0 + 4 hrs \\ T_0 + 8 hrs \\ T_0 + 12 hrs^3$
Urine Pregnancy Test(if applicable)	X	X				X
Best-corrected Visual Acuity (ETDRS)	X	X	X Pre-T ₀	X Pre-T ₀	X Pre-T ₀)	X Pre-T ₀)
Biomicroscopy	X	X	X Pre-T ₀ $T_0 + 2$ hrs $T_0 + 4$ hrs	X Pre-T ₀	X Pre-T ₀	X Pre-T ₀ , $T_0 + 2 \text{ hrs}$, To $+ 4 \text{ hrs}$

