5. STUDY VISIT PROCEDURES

All study visit procedures should be conducted in the order listed in Section 5.1.

Informed Consent: Properly executed informed consent (written and verbal) is to be obtained prior to completion of any study-related procedures. Subjects must review, sign, and date the informed consent document and receive a copy. The original document should be retained in the Investigator's Site File (ISF) or with the Subject's source documents.

Medical and Ocular History: Relevant and clinically significant medical and ocular history must be recorded. This includes reported changes between Screening Visit 1 and first IP administration.

Concomitant Medications/Procedures: All prescription and over-the-counter (OTC) medications and nutritional supplements taken during the study and 30 days prior to the Screening Visit will be recorded. Additionally, all ocular hypotensive medications taken within 45 days prior to the Screening Visit will be recorded. Diagnostic and anesthetic eye drops do not need to be recorded. All procedures occurring during the study and 30 days prior to the Screening Visit will be recorded.

Randomization: Randomization will be accomplished using an Interactive Web Response System (IWRS). Site personnel will receive instruction about IWRS access and use.

Adverse Events: Any events occurring after the first dose of IP will be recorded as an adverse event. At each visit, the subject should be asked questions such as, "How are you feeling? How are your eyes feeling today? Have you had any changes since the last exam?"

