7.4 Definition of Serious Adverse Event

An SAE is any experience that suggests a significant hazard, contraindication, side effect, or precaution. This includes any experience that:

- Results in death
- Is acutely life-threatening
- Requires in-patient hospitalization or prolongs the existing hospitalization
- Results in persistent or significant disability/incapacity
- Is a congenital anomaly/birth defect
- Requires medical or surgical intervention to prevent one of the outcomes listed above

Examples of such medical events include allergic bronchospasm requiring intensive treatment in an emergency room or at home, blood dyscrasias or convulsions that do not result in in-subject hospitalization, or the development of drug dependency or drug abuse. This definition includes concurrent illness or injuries, exacerbation of pre-existing conditions and AEs occurring as a result of drug withdrawal, abuse or overdose. Serious adverse events observed during all periods of a clinical study after the first dose of IP (Day 1) have been administered, are to be recorded, including those occurring during a period without study medication and whether or not the AE is judged to be related to the study medication.

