7.8 Definition of Relationship of Adverse Event to IP

The investigator's assessment of causality must be provided for all adverse events (serious and non-serious). The investigator must record the relationship and report such an assessment in

accordance with the serious AE reporting requirements, if applicable. An investigator's causality assessment is the determination of whether there exists a reasonable possibility that the investigational product caused or contributed to the adverse event. If the investigator does not know whether or not the investigational product caused the event, then the event will be handled as "related to investigational product" for reporting purposes, as defined by D. Western Therapeutics, Inc. If the investigator's causality assessment is "unknown but not related to investigational product," this should be clearly documented in study records.

In addition, if the investigator determines a serious adverse event is associated with study procedures, the investigator must record this causal relationship and report such an assessment in accordance with the serious adverse event reporting requirements, if applicable. The categories are as follows:

0=Unrelated: No temporal association, or the cause of the event has been

identified, or the drug, biological, or device cannot be

implicated.

1=Possibly Related: Temporal association, but other etiologies are likely to be the

cause; however, involvement of the drug, biological, or device

cannot be excluded.

2=Probably Related: Temporal association, other etiologies are possible, but

unlikely.

3=Definitely Related: Temporal association and no other etiologies possible.

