4.5 Washout Period

A listing including information on whether a subject enters the washout period or not, the type of used ocular hypotensive therapy and the length of the washout period will be created for each subject in the Safety Analysis Population.

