4.12.1 Adverse Events

Treatment-emergent adverse events (TEAE) are defined as AEs starting on or after the first dose of IP. A pre-existing event that worsens in severity after receiving the first dose of IP is treated as a new TEAE with date of onset set to the date of the increased severity. Summary tables will include TEAEs only. TEAEs will be summarized by treatment and overall. Non-treatment emergent AEs will be listed only.

An ocular event is an event where the site of the event is reported as both eyes (OU), right eye (OD) or left eye (OS).

Proportion of subjects reporting an event will be calculated based on the number of subjects in the corresponding treatment group. The 95% CI will be calculated using the Clopper-Pearson method.

The number and percentage of subjects reporting any event, any non-ocular event, and any ocular event will be summarized.

An overall summary table of TEAE will be provided by treatment group and location (non-ocular and ocular) for the following categories:

Confidential

- Number and percentage of subjects with a TEAE
- Number and percentage of subjects with a treatment-related TEAE
- Number and percentage of subjects with a TEAE leading to IP discontinuation
- Number and percentage of subjects with a TEAE leading to study discontinuation
- Number and percentage of subjects with a serious TEAE
- Number and percentage of subjects with a treatment-related serious TEAE
- Number and percentage of subjects with a TEAE leading to death

AEs will be coded using Medical Dictionary for Regulatory Activities (MedDRA) version 26 or higher. The following summaries will be provided:

- TEAEs by System Organ Class (SOC) and Preferred Term (PT)
- Serious TEAEs by SOC and PT
- TEAEs leading to IP discontinuation by SOC and PT
- TEAEs leading to study discontinuation by SOC and PT
- TEAE leading to death by SOC and PT
- TEAEs by SOC, PT, and maximum severity
- Treatment-related TEAEs by SOC and PT

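### A non-fatal serious event between consent and first dose, washout included, has no 24-hour SAE report, and the schedule and the SAP do not fit the rule that causes this

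*Protocol*

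**What the plan says.** The first-dose rule appears in several places in the protocol.

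- Section 7.1: "Any changes in health status after informed consent has been obtained, but prior to the first dose of IP, will be reported as medical history".
- Section 5, adverse events paragraph: "Any events occurring after the first dose of IP will be recorded as an adverse event".
- Section 5.1, Screening and Day 0 visit lists: "Any unfavorable medical occurrence should be reported as medical or ocular history". The Day 1 list says the same of pre-dose events, and the dilated ophthalmoscopy paragraph in Section 5 sends pre-dose changes to ocular history.
- Section 7.4 sets the same start for SAE recording: "Serious adverse events observed during all periods of a clinical study after the first dose of IP (Day 1) have been administered, are to be" (the quote stops just before its final verb). Section 7.10 does so for reporting SAEs to the sponsor.

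Other text points elsewhere. The Time and Events Schedule (protocol Table 1, repeated in SAP Appendix 1) has the row "Adverse Event Assessments X X X X X X", which marks all six visits, two of them wholly before dosing. Section 7.8 says that "if the investigator determines a serious adverse event is associated with study procedures, the investigator must record this causal relationship". SAP 4.12.1 states "Non-treatment emergent AEs will be listed only". Section 7.10 also sends all deaths in the study population to the SAE form within 24 hours, and that sentence names no starting point.

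On outputs, SAP 3.4.1 limits the Safety population to randomized subjects with at least one dose. SAP 4.7 (medical and ocular history) and 4.12 (all safety analyses) use that population. SAP 4.5 plans a listing of washout status, prior therapy and washout length, which "will be created for each subject in the Safety Analysis Population".

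**The concern.** Stopping IOP-lowering treatment is something the trial does to its subjects, for up to six weeks plus a one-week scheduling allowance. The protocol treats it as a risk: exclusion 17 keeps out subjects who could not safely stop, and Section 3.5 allows a switch to another agent on safety grounds. If a subject has a serious but non-fatal event because of the washout, a site following 7.1 enters it as history and sends no form.

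A history entry carries less information. Section 7.1 asks for severity, seriousness, relationship, treatment, action taken and outcome for adverse events. Section 5 asks only for relevant and clinically significant history, and SAP 4.7 tabulates it by SOC and PT together with pre-existing disease. The sponsor gets no expedited notice, and the Medical Monitor, whose review can lead to suspension under Section 12.4, learns of the event only through routine review. A subject who leaves the trial during washout because of such an event is in none of the populations for which the SAP describes event-level content.

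**Working it through.** **1. Length of the washout.** Section 3.5 gives up to 42 days plus 7, so 42 + 7 = 49 days. This agrees with the 49-day limit in the same section and with the Screening column of Table 1. Adding 28 treatment days gives 49 + 28 = 77 days, and 77/7 = 11.0 weeks, which reproduces the protocol's maximum participation of about 11 weeks.

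**2. Share of participation before adverse event and SAE capture starts.**
- Maximum washout: 49/77 = 64%.
- Maximum washout with the +2-day window at Day 28: 49/(49 + 30) = 62%.
- Washout without the extra week: 42/(42 + 28) = 60%.
- Minimum washout for muscarinic agonists or CAIs (5 days, Table 2): 5/(5 + 28) = 15%.

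Subjects on no ocular hypotensive therapy have no washout, but up to 42 days may still pass between Screening and Baseline.

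**3. Route of a pre-dose event through the protocol.**
- Non-serious: history (7.1, Section 5, 5.1).
- Serious, non-fatal: recording in 7.4 and reporting in 7.10 both begin after the first dose, so no form is required.
- Fatal: the deaths clause in 7.10 can be read to require the form within 24 hours.
- Serious and linked to a study procedure: 7.8 asks for the causal link to be recorded and reported, but as part of SAE reporting and only where applicable. It does not clearly override the start date in 7.4 and 7.10.

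**4. Consistency of the non-TEAE listing.** The protocol records an event as an adverse event only after the first dose. SAP 4.12.1 defines a TEAE as an adverse event starting on or after the first dose. Every new event that the protocol allows to be recorded therefore meets the TEAE definition, and the planned listing of non-treatment-emergent events has no new pre-dose event to show.

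**5. Outputs for a consented subject who is never dosed.**
- Medical and ocular history (SAP 4.7): not included.
- Washout listing (SAP 4.5): not included, and its content is therapy and duration, not events.
- Safety analyses, including adverse event listings (SAP 4.12): not included.
- Disposition (SAP 4.4): counts of consented subjects and of withdrawals with reason, but no event detail.

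**The case against.** The strongest reply is that this is one rule applied consistently. Section 5, Section 5.1, 7.1, 7.4 and 7.10 all start at the first dose, and 7.2 defines an adverse event in a subject who has been given a product. The Table 1 row can be read as the health question that 7.1 wants asked at every visit, with 5.1 saying where pre-dose answers go. Much of this stands. Starting non-serious adverse event capture at the first dose is a defensible choice, and for those events the row may be no worse than loosely labelled. The reply does not supply a route for a non-fatal serious event, and it does not explain the planned non-TEAE listing.

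A reader might also infer more than the text supports:

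- *That no pre-dose event of any kind reaches the SAE form.* The deaths clause in 7.10 has no first-dose limit.
- *That subjects go untreated for 49 days.* That figure is the longest washout. Section 3.5 allows another agent during a long washout, Section 4.4 allows topical CAIs for part of it, and some subjects need no washout.
- *That events in never-dosed subjects reach no output at all.* Disposition gives reasons for withdrawal, and SAP Section 6 puts the list of tables and listings in a separate document that is not available here.
- *That the sponsor's side would see nothing.* Section 12.4 provides for regular Medical Monitor review of all clinical data, and Section 10 for continual masked monitoring under a safety plan that is not available here. What is missing is the expedited report.
- *That 7.8 already settles the matter.* It concerns causality for an event already classed as an SAE.

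**Conclusion.** The point holds for non-fatal serious events between consent and first dose: the protocol requires no 24-hour report for them, whether or not the washout caused them. Two inconsistencies should be resolved with it, namely the adverse event row at Screening and Day 0 against 7.1, and the non-TEAE listing that the recording rule leaves without new pre-dose events. The SAP describes no event-level output for consented subjects who are never dosed.

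The 64% is a share of calendar time at the longest washout. It does not measure risk, events or subjects. The documents give neither a washout event rate nor an expected number of subjects lost before dosing, so the number affected cannot be estimated. The conclusion assumes that sites follow 7.1 as written and that neither the safety plan nor the listing specification adds a pre-dose SAE rule. No efficacy result and no TEAE table is affected; the gain is in subject safety and in the completeness of the study report.

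**What to change.** - **Protocol 7.1, 7.4 and 7.10:** report SAEs from informed consent, at minimum those related to the washout or to study procedures.
- **Section 5 and 5.1:** change the pre-dose recording text to match, in the adverse events and ophthalmoscopy paragraphs and in the Screening, Day 0 and Day 1 lists. Otherwise sites would still be told to file these events as history.
- **Section 7.2:** extend the adverse event definition so that it does not depend on a product having been given.
- **7.10 and 7.11:** restate the end of SAE follow-up so that it works for a never-dosed subject, for whom the Day 28 and last-dose anchors do not exist.
- **Table 1 and SAP Appendix 1:** reconcile the adverse event row with 7.1. Non-serious pre-dose events may stay as medical history if the row is relabelled to say so.
- **SAP 4.12 and 4.12.1:** list pre-dose SAEs and any other non-treatment-emergent events for all consented subjects, as a stated exception to the Safety-population rule. Leave the TEAE definition and tables unchanged.

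The cost is some extra SAE entries for screened subjects, one listing with a wider population, and coordinated edits to several protocol sections. No visit or procedure is added.

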7.2 Definition of Adverse Event

An AE is any unfavorable medical occurrence in a subject or clinical investigation subject administered a pharmaceutical product, which does not necessarily have a causal relationship with the treatment. An AE can, therefore, be any unfavorable and unintended sign, symptom, or disease temporally associated with the use of an investigational product, whether or not considered related to the investigational product. All AEs, including observed or volunteered problems, complaints, or symptoms, must be recorded. This definition also includes AEs which are reported up to 30 days after a subject has completed a clinical study. Therapeutic failures during clinical trials are not considered to be AEs.

Examples of adverse events include, but are not limited to:

 Abnormal test finding judged clinically significant by PI, and/or induces clinical signs or symptoms and/or requires active intervention and/or requires interruption or discontinuation of IP

- Clinically significant symptoms and signs
- Hypersensitivity
- Progression/worsening of underlying disease (not therapeutic failure of IP)
- Loss of > 3 lines BCVA
- Clinically significant change in pachymetry

Additionally, they may include the signs and symptoms resulting from:

- Drug overdose
- Drug withdrawal
- Drug abuse
- Drug misuse
- Drug interactions
- Exposure in utero (i.e., pregnancy within 30 days of study completion)

